SFS Statistical Analysis Plan
Household Intervention Study
Last Revised 10/8/19

Applicable to the following UW IRB Study Protocols:

Seattle Flu Study (SFS) **(6181)**

Household Intervention Study **(8200)**

Funding:

Brotman-Baty Institute, University of Washington

Table of Contents

A. STUDY OBJECTIVES AND SUMMARY	3
B. FINAL ANALYSIS PLAN	4
B1. ANALYSIS DATASETS	4
B2. BASELINE TABLES AND STUDY CONDUCT	5
Description of the main tables and statistical analyses	5
Study Accrual	5
Baseline Demographic Characteristics	5
Baseline Behavioral Characteristics	5
Baseline Influenza and Respiratory Illness Symptoms	5
Drug adherence	5
Retention	5
Follow-up	5
B3. SAFETY ANALYSIS	5
B4. ENDPOINT ANALYSIS	5
Primary Analysis	5
Secondary Analyses	5
Additional analyses with Influenza virus infection as the Endpoint	5
Additional analyses with other respiratory infections as Endpoints	5
Sensitivity Analyses	5
C1. INTERIM ANALYSIS PLAN	5
Original plan	5

A. Study Objectives and Summary

Purpose: To evaluate the efficacy of a home-based approach to influenza testing in households in order to shorten the time to diagnosis, antiviral delivery, and antiviral initiation and reduce influenza transmission within the household.

Design: This study is an open cohort intervention study with prospective exposure assessment. It is a pilot study of a home-based approach to influenza infection, utilizing self-test kits and rapid home delivery of baloxavir (BXM). All members of all households must be asymptomatic at enrollment.

Population: Households with at least 3 individuals residing there at least 4 days a week, including at least 2 household members that are eligible to take BXM, will be monitored throughout the influenza season for the onset of a cough.

Expected study size: This study will be conducted in up to 1,000 households in the Seattle, WA area.

Study duration: One influenza season, beginning November 1, 2019 and ending May 1, 2020.

Primary aim: Evaluate whether this home-based strategy leads to a large percentage of influenza-positive individuals initiating antiviral therapy within 48 hours of symptom onset.

Secondary aim: Determine the social and technical infrastructure that would be required to rapidly detect and interrupt influenza transmission at the household level and to determine whether a home-based self-test and antiviral delivery strategy would be feasible in the context of a pandemic.

Primary Objectives:

P1) To measure the proportion of individuals who are initiated on antiviral therapy within 48 hours of symptom onset using home-based self-test to diagnose influenza and home delivery of antivirals.

Secondary Objectives:

S1) Proportion of individuals who test positive for influenza using the home-based test within 48 hours of symptom onset

S2) Proportion of individuals who are delivered antivirals within 48 hours of symptom onset

S3) Symptom duration and severity among cases and household contacts

S4) Viral titer and duration of viral RNA detection among influenza-positive cases

S5) Cost effectiveness, assessed using health resource utilization and school and work absenteeism

S6) Emergence of antiviral resistance, assessed by genetic sequencing of influenza strains

B. Final Analysis Plan

This section describes the main statistical analyses that will be conducted on enrolled households at DSMB meetings and at the end of the study.

B1. Analysis Datasets

The Primary Dataset will consist of all individuals from enrolled households who enroll in the study, comprised of symptomatic (drug-eligible) individuals.

All eligible and enrolled households will be included in the study unless they meet one or more of the following exclusion criteria:

1. Previous documentation of an influenza infection prior to or during the annual influenza season in any household member prior to enrollment

At the participant level, enrolled individuals meeting any of the following criteria will be excluded from analysis (note: their household may still be eligible, as another eligible member of their household may still enroll):

1. The individual's informed consent is determined to be not valid
2. The individual has been double enrolled in the study. In this case, the individual's data will be used once.
3. No symptom questionnaire is collected.

B2. Variable definitions

[See Tables 1a-c for details]

B3. Baseline Tables and Study Conduct

Description of the main tables and statistical analyses

This section describes the main tables and statistical analyses. Metrics will be updated monthly and presented to the DSMB at each meeting.

Baseline sociodemographic and health characteristics

Table 1a will display baseline sociodemographic, health, and household-related characteristics of individuals enrolled in the study. Sociodemographic variables will include: age, sex, race, currently employed, highest level of educational attainment. Health variables will include: health insurance type, comorbidities, pregnant, lactating, any use of tobacco and/or e-cigarettes, and influenza vaccination history (for both this season and the previous season). Household-level variables will include: type of household, number of people sharing living space, number and ages of children in the household. Data will be presented both (1) overall and (2) by households with a case v. households with no cases. No formal statistical testing will be performed.

Follow-up behavioral and clinical characteristics

Table 1b will display follow-up behavioral and symptom characteristics of individuals enrolled in the study, based on the weekly symptom diary. Behavioral variables will include: daily activities affected by illness (includes school and work outcomes), number of days absent from school or work, office culture around (paid) sick time off, sought clinical care, behavioral/ hygiene change since received test result, recovery status from illness, and reason for not receiving vaccine. Symptom characteristics will include: positive test result, number of household members with influenza diagnosis in the past week, weekly temperature measurement, number of days sick, time since symptom onset, time between symptom onset and worst symptom presentation, symptoms and symptom severity (for each day with symptoms). Summary statistics appropriate

for the measurement scale will be used to describe the distribution of these variables. Data will be presented both (1) overall and (2) by households with a case v. households with no cases. No formal statistical testing will be performed.

Household-specific characteristics

Table 1c will describe characteristics of the households included in the study. Measures included in this table will include: location (based on address). Summary statistics appropriate for the measurement scale will be used to describe the distribution of these variables. Data will be presented both (1) overall and (2) by households with a case v. households with no cases. No formal statistical testing will be performed.

B4. Safety Analysis

Serious adverse events (SAEs)

A list of serious adverse events will be presented by shelter and by treatment v. intervention period. As defined in the study protocol, serious adverse events include death, a life-threatening reaction to the study drug (or placebo) or other study procedure, hospitalization, or significant or persistent disability or impairment. The incidence of SAE's (events/person-days of follow-up) will be presented both (1) overall and (2) by case v. non-cases. We will test for a difference in SAE rate between the two study periods (intervention v. control) using an exact Poisson test in R.

Baloxavir-resistant influenza transmission

Evidence of a strong intervention effect causing incidence of baloxavir-resistant influenza strains will be evaluated using linear mixed effects logistic regression. The unit of analysis will be influenza-positive tests, and the outcome will be binary: baloxavir-resistant or not baloxavir-resistant.

B5. Power sample size

Table 1. Sample size calculations: Number of clusters needed per arm for two-group cluster-randomized trial - Household intervention study

Effect size (% reduction in flu incidence)			
Power	0.30	0.40	0.50
0.80	57	84	129
0.90	76	112	172

All calculations above assume an ICC of 0.29, anticipated average (or actual) cluster size of 4, and a 15% transmission rate for flu.

Based on these calculations, an arm size of 250 households should be sufficient to detect a 30% reduction in flu incidence at 90% power.

B6. Endpoint Analyses

Primary Analysis

[figure not shown]
Question: Does this home-based self-test diagnostic tool and rapid treatment intervention lead to a large percentage of influenza-positive individuals initiating antiviral therapy within 48 hours of symptom onset?

Endpoint: Cumulative incidence of influenza virus infection

Measure of Association:
Cumulative Incidence (Attack Rate, Incidence Proportion)

$$\text{Cumulative Incidence} = \frac{\text{Number of participants that successfully initiate antiviral therapy within 48 hours of symptom onset (among participants who have a cough and self-test positive for influenza) during the October 2019-May 2020 influenza season}}{\text{Number of influenza-free participants at risk at } t_0 \text{ (baseline)}}$$

Relevant DAG

Exposure:

Exposed (Treatment) = Participants who develop cough and self-test positive
Unexposed (No treatment) = Participants who develop cough but self-test negative

Outcome:

Success = Participant initiated on antiviral therapy within 48 hours of symptom onset
Failure = Participant is not initiated on antiviral therapy (**more than 48 hours** after symptom onset *or* participant **never** initiates antiviral therapy)

Table 1. Estimated secondary attack rates for planned 2019-2020 study aim on household transmission dynamics.

The study is being conducted in the Seattle, WA area over one influenza season. The goal is to enroll at least 250 (up to 1,000) households. Of these, 25% are estimated to have an individual in the household diagnosed with influenza based on estimates from previous household studies.^{23, 28-29}

A table for influenza attack rates by household size is provided below.

Household attack rate	Total households enrolled	Primary cases	Secondary cases (mean household size 5)	Secondary cases (mean household size 4)	Secondary cases (mean household size 3)
25%	250	63	45-96	34-72	23-48

20%	250	50	36-76	27-57	18-38
10%	250	25	18-38	14-29	9-19
Mean household size includes case.					
Secondary attack rate 18-38%, secondary cases presented as a range based on these high and low bounds.³⁰⁻³²					

Incidence Density

Using time-specific variables such as date of enrollment, weekly symptom diaries and questionnaires, Incidence Density (ID) will be calculated, defined with the following formula:

Incidence Density =

Number of participants that successfully initiate antiviral therapy within 48 hours of symptom onset (among participants who have a cough and self-test positive for influenza)

Total person-days

Model

The proportion of individuals that 1) test positive and 2) receive and initiate treatment within 48 hours of symptom onset using home-based self-test and delivery methods will be analyzed with a binomial regression GLMM with a log link. The outcome follows a binomial distribution, with the number of successes in a series of n independent Bernoulli trials, where each trial has probability of success p . Successes here are defined as an individual successfully initiated on antiviral therapy within 48 hours of symptom onset using home-based self-test to diagnose influenza and home delivery of antivirals. The model is defined below:

Incidence proportions of influenza will be presented in tables.

A formal statistical comparisons between study periods (control vs. intervention) will be performed using a Wald test of the hypothesis

$H_0: RR=1$

$H_a: RR \neq 1$

The general form of the model (in matrix notation) is:

$$\mathbf{y} = \log\left(\frac{p}{1-p}\right) = \mathbf{X}\boldsymbol{\beta} + \mathbf{Z}\mathbf{u} + \boldsymbol{\epsilon}$$

Variable	Definition
\mathbf{y}	$N \times 1$ column vector, the outcome variable
\mathbf{X}	$N \times p$ matrix of the p predictor variables
$\boldsymbol{\beta}$	$p \times 1$ column vector of the fixed-effects regression coefficients (the β s)
\mathbf{Z}	$N \times q$ design matrix for the q random effects (the random complement to the fixed \mathbf{X})
\mathbf{u}	$q \times 1$ vector of the random effects (the random complement to the fixed $\boldsymbol{\beta}$)
$\boldsymbol{\epsilon}$	$N \times 1$ column vector of the residuals, that part of \mathbf{y} that is not explained by the model height

where each individual β value represents the change in log-odds of receiving and initiating treatment within 48 hours, that are associated with a particular demographic or clinical risk factor. A one-sided test with $\alpha = .05$ will be used. A table of the estimated Risk Ratios for a one unit increase in each covariate, given the other covariate values will be presented, along with the corresponding 95% confidence intervals, and p-values.

Data cleaning and analysis

All analyses will be performed in R version 3.6.1 using the package 'lme4.'

Secondary Analyses:

Question: How well does the self-test perform in comparison to the gold standard molecular test?

Sensitivity, specificity, PPV and NPV of the self-test will be calculated and compared to the gold standard molecular test. Table 2 (below) presents relevant formulas.

Table 2. Sensitivity, Specificity, PPV, and NPV of the Ellume Self-Test, SFS Household Intervention Study, 2019-2020 influenza season

Test Score	The Truth	
	Has Influenza	Does Not Have Influenza
Positive	True Positives (TP) a	False Positives (FP) b
Negative	False Negatives (FN) c	True Negatives (TN) d

$$\text{Sensitivity} = \frac{TP}{TP+FN} = \frac{a}{a+c} \quad \text{Specificity} = \frac{TN}{TN+FP} = \frac{d}{d+b}$$

$$\text{PPV} = \frac{TP}{TP+FP} = \frac{a}{a+b} \quad \text{NPV} = \frac{TN}{TN+FN} = \frac{d}{d+c}$$

Question: What is the association between influenza infection and: (1) influenza strain (by genetic sequencing) and (2) viral kinetics (maximum titer, duration viral RNA detection)?

Sensitivity analysis

Sensitivity analyses will be performed to explore the uniformity of any treatment effects found in the overall analysis.

Question: Does influenza incidence change when we look at varying testing timepoints (e.g. testing within 24, 48, and 72 hours of symptom onset)?

Details:

A sensitivity analysis will be performed to assess the effect of delayed testing on the intervention effect. The model will be re-run with three subsets of the data: those that were treated within 24, 48, and 72 hours of symptom onset. This will then be further analyzed with a time*age interaction. For example, we might expect that a 13-year-old might have more detectable RNA virus than an older adult at the same time point.

Data cleaning and software

All analyses will be performed in R version 3.6.1 using packages `'lme4'` and `'swCRTdesign'`.

C. Interim Analysis Plan

Original Plan

The DSMB will meet every month to review study progress and other issues as outlined below. In the proposed 6 month study, it is expected that the DSMB will meet X times.

Study progress and validity

At each monthly visit the DSMB will review data on enrollment, adherence of both households and household members, and all protocol violations. The DSMB will also compare the (pooled) observed influenza incidence rate to the (pooled) expected influenza rate to determine if the influenza incidence rate among study participants is at least as great as the incidence rate assumed in the study design, since incidence varies by influenza season. The DSMB will recommend any changes to the study design they believe are needed to ensure study validity.

Expected event rate: 150/1000 pdy in the control period and 120/1000 pdy in the intervention period; 135/1000 pdy overall.

Efficacy monitoring

Baloxavir-resistant influenza strain transmission

Additional testing and sequencing of non-influenza respiratory pathogens will also occur. Baloxavir resistance will be analyzed via interim analyses and monitored for the duration of the study. In the unlikely event that the incidence of the transmission of baloxavir-resistant strains of flu exceeds 20% of study participants, the study will be halted.

Tables and Figures

Table 1a. Sociodemographic characteristics of individual participants, SFS Household Intervention Study, 2019-2020 influenza season

Variable	Full sample n=	Cases only n=
Sociodemographic variables		
Age - median (range)		
Sex		
Male		
Female		
Race		
American Indian or Alaska Native		
Native Hawaiian or other Pacific Islander		
Black or African American		
White		
Multiple Races		
Other		
Prefer not to say		
Currently employed		
Yes		
No		
Education		
Less than high school		
High school or GED		
Some college		
Bachelor's degree		
Advanced degree		
Prefer not to say		

Household variables		
Household structure House/condo/townhouse Shelter Apartment Dormitory Assisted living facility Skilled nursing center No consistent primary residence Other		
Number of people sharing living space I live by myself 2 people 3 people 4 people 5 people 6 or more people Do Not Know Prefer Not to Say		
Age groups of children in household No children Age 0-5 Age 6-12 Age >12		
Health insurance Private Government Other None Prefer Not to Say		
Health variables		
Cigarette and e-cigarette use Tobacco products (e.g. cigarettes, cigars, pipes) Electronic cigarettes/vapor pens No Prefer not to say		
Pregnant Yes No		
Received Influenza <small>View Menu</small> ne 2019-2020 season 2020-2021 season		
Comorbidities		

Values are n (%), or median (range) for continuous age distributions.

References

<https://jamanetwork.com/journals/jama/article-abstract/193547>

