5. Following the prescription, the study pharmacist will dispense and package the BXM. Additionally, an informational hand out regarding the BXM dosing instructions will be included in this package. Furthermore, the individual will receive a post-visit Care Plan through the tele-health app, which will include reminders about the next steps for the study.
6. Following packaging of the study drug, a rapid delivery service will be notified that the intervention is available for delivery.

7. Next, rapid delivery service will pick up the study drug and deliver it in-person to the household of the case.
8. After delivery, the case will take the study drug and record the time of ingestion in the illness questionnaire in REDCap.

Follow-up

Following drug receipt, individuals will be screened 48 hours later to determine whether there is evidence of short-term reaction to the drug. Any short-term evidence reaction to the drug will be treated promptly by consultation with a member of the study medical expert team. In addition, the household will receive the contact information for a medical professional for follow-up questions after initiation of the intervention. Furthermore, the drug eligible participant will also be able to direct drug related questions to a tele-health provider via the tele-health app.

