- 20 mg white to light yellow, oblong shaped film-coated tablets debossed with “Ø772” on one side and “20” on the other side available as:
 - 2 x 20 mg tablets per blister card in secondary packaging: NDC 50242-828-02
 - 4 x 20 mg tablets per blister card in secondary packaging: NDC 50242-828-02
- 40 mg white to light yellow, oblong shaped film-cated tablets debossed with “BXM40” on one side available as:
 - 1 x 40 mg tablet per blister card in secondary package: NDC 50242-860-01
 - 2 x 40 mg tablets per blister card in secondary packaging: NDC 50242-860-02

Upon receiving a prescription for antiviral medication from a tele-health provider, a study pharmacist will pull the blister pack or packs from the correct weight bin, which will be organized prior to the start of the influenza season, and dispense the medication.

Following the packaging and labeling of the intervention, an informational hand out about the study drug will be included in this packaging along with the contact information for a licensed medical professional associated with the study who is available to answer any follow-up questions the participant may have regarding the intervention. Furthermore, the drug eligible participant will also be able to direct drug related questions to a 98point provider via the tele-health app.

Medication delivery and counseling

After the intervention is dispensed, the rapid delivery service will be notified that the study drug is available for delivery. Next, the rapid delivery service will pick up the intervention and deliver the package to the household of the case within 2-6 hours of an influenza diagnosis . Once the medication leaves the storage facility, delivery tracking will be performed by a member of the study staff and a log recording successful medication delivery will be kept as additional quality assurance measure.

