Person-to-person transmission: We will use the CDC definition for influenza transmission that refers to the ability of an influenza virus to spread from one person to another, most commonly through large or small droplets containing influenza virus that are expelled when a sick person is coughing or sneezing.

XI. Statistical Analyses

The primary objective is to precisely estimate the proportion of drug eligible individuals with an influenza diagnosis who initiate treatment within 48 hours. We define precision in terms of the width of a 95% confidence interval. The width of a 95% CI will be less than or equal to $\pm 1.96 \cdot 0.5/\sqrt{n}$ where n is the number of individuals who test positive for flu. With 250 households participating and an attack rate of 25% we expect 63 individuals with confirmed influenza infection. This will give a 95% CI for the proportion initiating treatment of ± 0.12 or less.

The proportion of drug eligible individuals receiving the drug and initiating treatment within 48 hours of symptom onset using home-based self-test and delivery methods will be estimated. Binomial regression with log link will be used to calculate the relative risk of receiving and initiating treatment within 48 hours by demographic and clinical factors, including age, sex, race/ethnicity, symptom types, symptom severity, and duration of symptoms. The RR, 95% confidence intervals and p-values will be reported.

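### The SAP aims to shorten times to diagnosis, delivery and initiation, but no planned analysis takes time to self-test, delivery or ingestion as its outcome

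*SAP*

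**What the plan says.** SAP section A gives the purpose as a home-based approach "in order to shorten the time to diagnosis, antiviral delivery, and antiviral initiation and reduce influenza transmission within the household". The objectives below it are proportions at a single time:

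- Primary (P1): "To measure the proportion of individuals who are initiated on antiviral therapy within 48 hours of symptom onset".
- Secondary (S1): "Proportion of individuals who test positive for influenza using the home-based test within 48 hours of symptom onset".
- Secondary (S2): "Proportion of individuals who are delivered antivirals within 48 hours of symptom onset".

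The endpoint list in Protocol section III has the same form. In SAP B6 the outcome is success or failure at 48 hours: "Failure = Participant is not initiated on antiviral therapy", a category that covers both later initiation and no initiation. For risk factors, Protocol section XI says: "Binomial regression with log link will be used to calculate the relative risk of receiving and initiating treatment within 48 hours". It names six: age, sex, race/ethnicity, symptom types, symptom severity and duration of symptoms.

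The times are largely there. The participant is to "record the time of ingestion in the illness questionnaire in REDCap" (Protocol V, Onset of Symptoms), Protocol Table 1 includes the timing of drug receipt, and "a log recording successful medication delivery will be kept" (Protocol V, Medication delivery and counseling). Kaplan-Meier and Cox methods appear in Protocol XI, but only for symptom resolution and duration of viral RNA detection.

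**The concern.** The purpose concerns intervals, and the analysis sees only whether each person was on one side of 48 hours. A dose at 6 hours and one at 47 hours count the same, as do a dose at 49 hours and none at all. The Protocol also sets a delivery target of 2-6 hours after diagnosis, which no listed endpoint measures. The secondary aim, to learn what infrastructure rapid detection and interruption would need, calls for the length of each step.

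The factor model has a related weakness. The study hypothesises that a large percentage will start within 48 hours. The better that holds, the fewer failures remain to distinguish six factors.

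**Working it through.** **1. The plan's own figure.** Cases: 250 × 0.25 = 62.5, rounded to 63. Maximum 95% half-width: 1.96 × 0.5/√63 = 0.1235, which agrees with the stated 0.12 after rounding. This supports estimating the proportion. The plan makes no power claim for the factors.

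**2. Failures available to the factor model.** Failures = n × (1 − p), where p is the proportion treated within 48 hours. The documents give no p, so it is an assumption.

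| Cases | Assumed success | Failures |
|---|---|---|
| 63 | 50% | 31.5 |
| 63 | 76-87% | about 15 to 8 |
| 63 | 90% | 6.3 |
| 50 (20% attack rate) | 75-85% | 12.5 to 7.5 |
| 250 (1,000 households × 25%) | 75-87% | about 63 to 33 |

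With 63 cases, six factors at one parameter each leave 8/6 = 1.3 to 15/6 = 2.5 failures per parameter. Factors with several categories lower this further.

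The denominator is itself uncertain. Protocol III requires drug-eligible, self-test-positive and laboratory-confirmed cases, which may be fewer than 63. Later cases in a household that has already received drug would, if counted, add failures.

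**3. Do the planned re-runs fill the gap?** The SAP sensitivity analysis re-runs the model in those treated within 24, 48 and 72 hours. As worded, everyone in the first two subsets is already a 48-hour success, so the outcome cannot vary. The 72-hour subset omits the never-treated. The SAP's incidence density divides 48-hour successes by total person-days, which is not an onset-to-dose time.

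**4. What a time-based comparison would gain.** Assumptions: 63 cases in two equal groups, log-normal time to dose with median 24-28 hours and log-SD 0.5, a factor that lengthens time 1.5-fold, two-sided 0.05, 2,000 simulated trials per setting. The 48-hour comparison is a pooled two-proportion test. The time comparison is a Mann-Whitney test with never-treated people ranked last.

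| Never treated | Rank power | 48-hour power |
|---|---|---|
| 5-10% | about 68-79% | 21-46% |
| 20% | 45-47% | 15-23% |
| 30% | about 32% | 12-19% |
| 40% | 18-20% | 9-12% |

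If 24-28 hours is instead the faster group's median, the figures at 5-10% never treated are 68-78% against 38-58%. If the factor changes only whether drug is obtained (5% against 30% never treated), the order reverses: about 40% for ranks and 50-59% at 48 hours.

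**5. A different model as a check.** Under proportional hazards with 63 cases, a 50/50 factor, hazard ratio 2.2 and 76-87% success, simulated power is 0.77-0.82 for a log-rank test and 0.67-0.70 at 48 hours. At 50% success the formula values are 0.60 and 0.57, so the gain nearly vanishes.

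**The case against.** The 48-hour cut is not arbitrary. It is the primary objective, the limit in the product description that the Protocol quotes, and the symptom-duration gate for testing and drug. The stated aim is to estimate a proportion precisely. All of that stands, and the primary endpoint should not change.

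Three stronger readings are tempting, and the documents do not support them.

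- A reader might infer that a 48-hour yes/no is the only thing analysed. The SAP also plans the 24/48/72-hour re-runs and a descriptive time since symptom onset in Table 1b. The Protocol uses initiation time to form early and late groups for symptom and cost comparisons. None of these makes time to a step the outcome, but they are not nothing.
- A reader might infer that the plan cannot show where the chain fails. The separate 48-hour proportions for positive self-test, delivery and administration do show where people drop out by 48 hours. What is missing is the duration of each step.
- A reader might infer that a time analysis should replace the 48-hour factor model. The 5-10% never-treated scenario favours that view, but the plan itself creates never-treated cases: one course per household, and a telehealth provider who may decline treatment. The gain shrinks as they increase, and it reverses for factors that act on access alone.

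The <48-hour gate limits late times. With nobody treated after 54 hours (assumed), ranks still led at 63 cases, with about 70-80% power against 21-41%.

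**Conclusion.** The point holds as a cheap improvement and is not a flaw in the primary endpoint. The stated purpose is about times, the main times are recorded or needed for planned endpoints, suitable methods are already in the plan, and no analysis applies them to self-test, delivery or ingestion.

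The figure of about 8-15 failures for six factors is a scenario (63 cases, 76-87% success), not a plan figure. At the SAP's ceiling of 1,000 households, similar success rates give about 33-63. The power advantage of a time-based analysis is real when a factor mainly stretches time and few people go untreated. It is small or reversed otherwise, which is why the two analyses belong side by side. Because the study has no comparator, either one describes delay and neither can show that delay was shortened.

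**What to change.** In the SAP:

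1. Keep the 48-hour proportion as primary. Keep the 48-hour relative risks and label them exploratory.
2. In all confirmed drug-eligible cases, add cumulative-incidence curves and medians for time from onset to self-test, delivery and ingestion. Keep never-treated people in the denominator as not reaching the step.
3. Add the telehealth diagnosis step if its time is captured. The documents do not say that it is, so confirm this, and confirm that onset and self-test are recorded finely enough to give hours.
4. Add a time-based factor analysis beside the 48-hour model, with an explicit rule for never-treated people, for example ranking them last. Leave out symptom duration if it means duration at testing, because it is then part of the onset-to-dose time.
5. Reword the 24/48/72-hour re-runs so that everyone stays in the denominator and only the cut-point moves.

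The cost is SAP wording, modest extra analysis, and a second effect scale to report beside the relative risks. Delivery and ingestion times need no new data collection.
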